11.3 Medical Monitoring

Medical Monitoring is provided by the study PI [name] and Co-Investigator [name]. For any medical concerns or questions regarding eligibility or safety please contact [contact].

SAEs need to be reported within 24 hours of the local PI becoming aware of the event.

12 DISCONTINUATION AND REPLACEMENT OF SUBJECTS

12.1 Early Discontinuation of Study Treatment

A subject may be discontinued from study treatment at any time if the subject, the investigator, or the study PI feels that it is not in the subject's best interest to continue.

All subjects are free to withdraw from protocol therapy at any time, for any reason, specified or unspecified, and without prejudice.

The following is a list of possible reasons for ***study treatment discontinuation***:

- a) Subject withdrawal of consent (or assent) – see section 12.2
- b) Subject is not compliant with study procedures
- c) Adverse event that in the opinion of the investigator would be in the best interest of the subject to discontinue study treatment
- d) Administration of rescue medication or ITP-directed therapy prior to Week 12 other than those permitted by the study protocol (see section 7.2.1), including for emergent intervention in the event of severe or uncontrolled bleeding.
- e) Lost to follow-up – see section 12.2
- f) Positive pregnancy test (females)
- g) Change in diagnosis: patient no longer has diagnosis of primary ITP – see section 12.2
- h) Death – see section 12.2
- i) Completion of protocol therapy

If a subject is discontinued from treatment due to an adverse event, the subject will be followed and treated by the Investigator until the abnormal parameter or symptom has resolved or stabilized.

All subjects who discontinue study treatment should come in for an early discontinuation visit as soon as possible. **Unless they are withdrawn from the study (see section 12.2) subjects should complete all remaining scheduled visits and procedures.**

All subjects are free to withdraw from participation at any time, for any reason, specified or unspecified, and without prejudice.

Reasonable attempts will be made by the investigator to provide a reason for subject withdrawals. The reason for the subject's withdrawal from the study will be specified in the subject's source documents.

12.2 Withdrawal of Subjects from the Study

All data collected up until the time of subject withdrawal will remain part of the study. Subjects will be followed for 30 days after the last dose of study drug.

Reasonable attempts will be made by the investigator to provide a reason for subject withdrawals. The reason for the subject's withdrawal from the study will be specified in the subject's source documents. As noted above, subjects who discontinue study treatment early (i.e., they withdraw prior to Week 12) should have an early

discontinuation visit. Subjects who withdraw after Week 12 but prior to 1 year should be encouraged to come in for a final visit (and the procedures to be followed would include those for their next scheduled visit).

Reasons for withdrawal from the study are:

- a) Subject withdrawal of consent for data submission
- b) Lost to follow-up
- c) Death
- d) Subject no longer has diagnosis of primary ITP

Otherwise, all subjects should be followed for collection of data to assess the protocol objectives.

12.3 Replacement of Subjects

A subject who withdraws from the study after enrollment and randomization will not be replaced.

13 PROTOCOL VARIANCES AND DEVIATIONS

Protocol deviations are defined as unintended variances from the approved protocol. The term deviation is often used in contrast to a violation, which is usually seen as more serious than a deviation.

Participating sites should report deviations to the coordinating center and BCM PI/designee as soon as possible and to their institution's IRBs per that site's institutional guidelines.

Participating sites in addition to their local requirement will be required to complete the variance form (see Manual of Operations) for all protocol deviations, and send to Baylor College of Medicine and Boston Children's Hospital Coordinating Center as soon as identified and not later than 5 days of occurrence.

As needed, the BCM PI or designee will report these protocol variances to the BCM IRB per local policies and to other regulatory agencies as applicable.

All serious adverse events and any unanticipated problems involving risk to subjects or others (UPIRSOs) that meet reporting criteria as defined by the BCM IRB as IRB of record will be submitted to the BCM IRB per their policy. Expected adverse events will not be reported. Expected adverse events are those adverse events that are listed or characterized in the Package Insert (P.I) or current Investigator Brochure (I.B).

A protocol variance or deviation occurs when the subject or investigator fails to adhere to significant protocol requirements affecting the inclusion, exclusion, subject

safety and primary endpoint criteria. Protocol deviations for this study include, but are not limited to, the following:

Failure to meet inclusion/exclusion criteria

Use of a prohibited concomitant medication

Failure to comply with Good Clinical Practice (GCP) guidelines will also result in a protocol violation. ICON will determine if a protocol violation will result in withdrawal of a subject.

When an event occurs, it will be discussed with the investigator and a Protocol Deviation/Variance Form detailing the event will be generated. Baylor College of Medicine will determine if the event qualifies as UPIRSO that meet reporting criteria as defined by the BCM IRB.

14 DATA SAFETY MONITORING

The Boston Children's Hospital will establish a Data Safety Monitoring Committee (DSMC) to review data relating to safety and efficacy, to conduct and review interim analyses, and to ensure the continued scientific validity and merit of the study, according to a DSMC Charter to be established for this protocol. There will be 2 interim review(s) conducted by the DSMC for the purpose of monitoring study conduct and assessing patient safety. Further details regarding the timing and content of the interim reviews is included in the statistical section below.

15 STEERING COMMITTEE

A Study Steering Committee (SSC) will be appointed.

The SSC will ensure transparent management of the study according to the protocol by recommending and approving study modifications as the need arises. The SSC will review protocol amendments as appropriate. Together with the clinical trial team, the SSC will also develop recommendations for publications of study results. The SSC will consist of investigators participating in the trial and representatives from the Clinical Trial Team.

Other members may be added after consultation with SSC members.

16 STATISTICAL METHODS AND CONSIDERATIONS

Overview

This is a prospective, open label, randomized, two-arm, multi-center Phase 3 trial. Enrolled patients with newly diagnosed ITP are randomized at enrollment 2:1 to the experimental treatment arm (eltrombopag) and standard treatment arm (investigator's choice of 3 standard therapies); randomization will be stratified by patient's age at enrollment and up-front treatment status, with block size of 3. Each stratum will be limited to a maximum of 27 patients. Hence, the age distribution of the final accrued cohort may not be representative of the patient population. This is appropriate in the context of this study to ensure sufficient number of patients to study treatment effects in each age group. The primary objective is to determine

whether the proportion of patients with platelet response is greater in the experimental treatment arm compared to the standard therapy arm using a one-sided Cochran-Mantel-Haenszel (CMH) test at alpha=0.025 (see section 16.b).

Intent-to-Treat and Evaluability

For the primary objective, all randomized patients will be included in an intent-to-treat (ITT) analysis. Evaluability for the secondary and exploratory objectives: In the experimental treatment arm, patients will be considered evaluable if they receive at least one dose of eltrombopag. In the standard treatment arm, patients will be considered evaluable if they receive at least one dose of one of the standard of care treatments.

Statistical Analysis

a. Baseline Demographic and Clinical Characteristics

Patient demographic and clinical characteristics at study enrollment will be summarized using descriptive statistics, including frequencies and proportions for categorical measures, and means, medians, ranges, and standard errors for continuous measures.

b. Analysis of Primary Endpoint

To address the primary objective, we will first test for normality of the distribution of the proportion of platelet responders. If the assumption of normality is upheld, a one-sided Cochran-Mantel-Haenszel (CMH) test, at alpha=0.025, will be used to compare the proportion of platelet responders between the two arms. If the normality assumption is violated, then a one-sided Fisher's exact test will be used. The monitoring boundaries and levels of significance for the interim and final analyses of the primary endpoint are detailed in Table 16A. If a monitoring boundary is crossed in an interim analysis, an independent Data Safety Monitoring Board (DSMB) will make a non-binding recommendation regarding trial conduct or potential closure. In the final analysis, we will reject the null hypothesis if the upper (efficacy) boundary z-value of 1.99302 is crossed; in that case, it will be reasonable to conclude that the rate of platelet response is significantly greater in patients treated with eltrombopag than standard first-line treatments. Otherwise, we will conclude that there is insufficient evidence to support superiority of eltrombopag over standard first-line treatments. All randomized patients will be analyzed in the ITT analysis.

Selection of platelet measurements for the determination of platelet response.

All platelet counts will be reported, and the four measurements closest in time to Weeks 6, 8, 10, and 12 will be selected for the determination of the primary endpoint. Within a sliding one-week window, only one measurement can be selected. Patients who have <3 platelet measurements due to missing data will be classified as non-responders.

c. Analysis of Secondary Endpoints

Analyses of all secondary endpoints will be performed in the subset of evaluable patients. To determine the effects of missing data, sensitivity analyses will be performed using two approaches: a) assuming missing at random; and, b) assuming missing not at random. For each secondary endpoint, the assumption of normality will be tested. If violated for binary endpoints, a Fisher's exact test will be used. If violated for continuous endpoints, a Wilcoxon rank-sum test will be used.

To address secondary objective 3.2.1, the Cochran-Mantel-Haenszel test will be used to compare the proportion of patients with poor WHO Bleeding Score and poor Modified Buchanan Score between the two arms.

To address secondary objective 3.2.2, an ANCOVA model will be used to compare the number of rescue therapies between the two arms.

To address secondary objective 3.2.3, the observed proportion and 95% confidence interval of platelet responders will be calculated in the subset of patients who required a rescue treatment during weeks 1-2 of the study.

To address secondary objective 3.2.4, the Cochran-Mantel-Haenszel test will be used to compare the proportion of patients who do not need ongoing treatment at 12 weeks and 6 months between the two arms.

To address secondary objective 3.2.5, the Cochran-Mantel-Haenszel test will be used to compare the proportion of patients with a treatment response at one year between the two arms.

To address secondary objective 3.2.6, an ANCOVA model will be used to compare the number of 2nd-line therapies between the two arms

To address secondary objective 3.2.7, an ANCOVA model will be used to compare the absolute change from baseline in percentage of regulatory T cells at 12 weeks and 1 year between the two arms

To address secondary objective 3.2.8, KIT scores will be calculated as per the methods described in Klaassen et al.²⁸ Spaghetti plots will be used to visualize the KIT scores over time per patient by treatment arm. An ANCOVA model will be used to compare the absolute change from baseline in KIT overall score at 1 week, 4 weeks, 12 weeks, and 1 year between the two arms. An ANCOVA model will be used to compare the Change Scale score at 1 week, 4 weeks, 12 weeks, and 1 year between the two arms.

To address secondary objective 3.2.9, fatigue scores will be calculated as per the methods described in Hockenberry et al.²⁹ All measures will be rescaled from 0 (no fatigue) to 100 (high fatigue) for consistency in scoring. Spaghetti plots will be used to visualize the fatigue scores over time per patient by treatment arm. The PROMIS tired question: “My child (I) got tired easily never to almost always” will be used as an anchor with severe fatigue defined as “often” or “almost always” with moderate fatigue being “sometimes”. An ANCOVA model will be used to compare the absolute change from baseline in fatigue at 1 week, 4 weeks, 12 weeks, and 1 year between the two arms.

To address secondary objective 3.2.10, an ANCOVA model will be used to compare iron indices at 12 weeks, 6 months, and 1 year between the two arms

To address secondary objective 3.2.11, the frequency and proportion (with 95% confidence interval) of patients with abnormal LFTs will be calculated. Adverse event rates will be coded by body system and MedDra classification term. Adverse events and serious adverse events will be tabulated by treatment group and will include the number of patients for whom the event occurred, the rate of occurrence, and the severity and relationship to study drug. If a patient experiences the same toxicity multiple times, a patient will be counted only once for a given toxicity at the maximum grade.

d. Analysis of Exploratory Objectives

Exploratory objectives are hypothesis-generating only. Any exploratory findings need to be confirmed in an independent study.

To address the platelet exploratory objectives 3.3.1, a Cochran-Mantel-Haenszel test will be used to compare the proportion of patients between treatment arms with: (1) specific platelet-defined treatment response at 12 weeks, (2) extreme thrombocytosis, and (3) loss of treatment response (in the subgroup of patients who achieved treatment response during the first 12 weeks. Cumulative incidence curves by treatment arm will be created to describe: (1) time to response and (2) time to platelet and bleeding response. Gray's test will be used to compare the cumulative incidence between treatment arms.

To address the patient-reported outcomes exploratory objectives 3.3.2, KIT scores and fatigue scores will be calculated as described. Spaghetti plots will be used to visualize the scores over time per patient by treatment arm. An ANCOVA model will be used to compare the absolute change from baseline at 1 week, 4 weeks, 12 weeks, and 1 year between the two arms.

To analyze the non-survey endpoints of exploratory objective 3.3.3, a Cochran-Mantel-Haenszel test (for categorical outcomes) or an ANCOVA model (for

continuous outcomes, like the cost of therapy) will be used to compare the two arms.

To address the survey-related aspects of exploratory objectives 3.3.3, the PROMIS® measures will be scored as according to the described approach ²². Mixed-effects model and the generalized estimating equations (GEE) allow for covariate adjustment and can model both within group effects (time) and between group effects ³⁰. The results will be summarized with adjusted means with associated 95% confidence intervals at each time point for each treatment group. For the primary analysis, these models will include the main effect of time (T0-T2). PHIS is a confidential database that allows use among the 47 member hospitals including a number of prominent pediatric hematology centers that participate in ICON. Descriptive analysis will be performed using PHIS data after patients have been identified using PHIS diagnosis codes to identify patients with ITP. Descriptive statistics will be performed to analyze financial burden measures. As instruments have not been validated, item level comparisons will be made between standard therapy and eltrombopag.

During the trial, on an ongoing basis the study team will monitor the response rate to each of the surveys. A patient will be counted as having responded to a given survey if both the baseline survey and at least one post-baseline survey are submitted. If the observed response rate for a given survey falls below 33%, the study team may consider halting the collection of that survey from subsequent patients, as it is an inappropriate use of resources, and unfair to patients, to continue to require survey submission if the survey data will be too sparse to address the study objective.

e. Interim Analysis

Interim analysis for efficacy and futility

To monitor for early evidence of efficacy or lack of efficacy (futility), we will perform group sequential analyses for a total of three “looks” at the data. Power calculations were performed using PASS 14 (NCSS, LLC. Kaysville, Utah, USA). We will conduct two interim analyses using a two-sided Cochran-Mantel-Haenszel test to compare the proportion of platelet responders between the two treatment arms, after 33% and after 67% of randomized patients are accrued. If the trial has not been terminated due to efficacy or futility, the third and final analysis will be conducted after accrual of all randomized patients at the end of the trial. We used the O’Brien-Fleming spending function to determine the monitoring boundaries for these three group sequential tests (Table 16A, Figure 1). For interim analysis 1, significant evidence that the experimental drug is more efficacious than the standard of care will have been provided if we observe a z-test statistic ≥ 3.71 . Significant evidence that the experimental drug is less efficacious than the standard therapy will have been provided if $z \leq -3.71$. For

interim analysis 2, significant evidence that the experimental drug is efficacious or not will have been provided if $z \geq 2.51$ or ≤ -2.51 , respectively. For the final analysis, significant evidence of the efficacy of the experimental drug will have been provided if $z \geq 1.99302$. The members of the study committee will remain masked to the results of the interim analyses. Because the results of this trial will set a new standard of care for this patient population, an independent Data Safety Monitoring Board (DSMB) will make a non-binding recommendation if/when it is appropriate to close the trial early on the basis of the statistical evidence.

[figure not shown]
Table 16A: Interim analysis monitoring boundaries and operating characteristics

Look	Proportion accrued	Lower Bndry	Upper Bndry	Nominal Alpha	Alpha Spent	Total Alpha	Power Spent	Total Power
1	0.33	-3.7103	3.7103	0.0002	0.0002	0.0002	0.02009	0.0201
2	0.67	-2.51142	2.51142	0.012	0.0119	0.0121	0.41425	0.4343
3	1	-1.99302	1.99302	0.0463	0.0379	0.05	0.38006	0.8144

Definitions:

- Nominal alpha: the significance level to be used for a single, standalone test at each interim test.
- Alpha spent: the amount of alpha spent by this interim test.
- Total alpha: the total amount of alpha that is used up to and including the current test.
- Power spent: the probability that the significance is found and the trial is stopped, given the alternative hypothesis (also called “exit probabilities”).
- Total power: these are the cumulative power values.

Figure 1. O’Brien-Fleming interim monitoring efficacy (red) and futility (green) boundaries for the rate of sustained of platelet response, comparing the eltrombopag arm to the standard of care arm using a two-sided Cochran-Mantel-Haenszel test

Interim analyses for safety

AEs and SAEs will also be reviewed at interim analysis 1 and 2. If any toxic deaths, or 2 intracranial hemorrhages, or 2 unprovoked thromboses are found at the first interim analysis, study will be temporarily halted to accrual for further evaluation.

f. Sample Size and Study Duration

Power Calculations for the Primary Objective

147 “informative” (as defined below) patients, randomized 2:1 to the experimental treatment arm and standard treatment arm, will be required to provide 81.4% power to detect an absolute difference of 25% in the proportion of patients who are platelet responders, assuming the response rate is 75% in the experimental treatment arm and 50% in the standard treatment arm, using a one-sided Cochran-Mantel-Haenszel (CMH) test and a type I error rate of 0.025. In order to provide at least 147 informative patients, up to 162 patients will be enrolled and randomized.

The first time point at which the primary endpoint, platelet response, will be assessed is 5 weeks after enrollment. A small number of patients, approximately

9%, are anticipated to withdraw from the study (i.e., withdraw from protocol therapy AND data submission) prior to the 5-week platelet assessment. It is reasonable to assume that the study withdrawal rate will be similar across the treatment arms. These patients are non-informative for the primary objective to assess the efficacy of eltrombopag; such patients dilute the treatment effect and as a result the power is diminished. These “non-informative” patients will be classified as non-responders and included in the ITT analysis. We will assume that 9% of randomized patients, a conservatively high estimate, will be non-informative. To account for the diluting effect the non-informative patients have on the comparison of response rates, we plan to enroll and randomize up to an additional 15 patients (~9%).

Total sample size and study duration

In summary, a total of up to 162 (estimated: 147 informative + 15 non-informative) patients will be enrolled and randomized 2:1 to the experimental treatment arm (N=108) and standard treatment arm (N=54). All randomized patients will be included in the ITT analysis of the primary objective.

We anticipate enrolling 45 patients per year (3.7 patients per month). The total accrual duration is expected to be about 3 years, plus 1 year follow-up on the last patient, for a total study duration of 4 years.

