5 CRITERIA FOR EVALUATION

5.1 Primary Efficacy Endpoint

The primary endpoint is binary, with each patient classified as either a platelet responder or a platelet non-responder. Platelet responders are defined as patients with ≥ 3 of 4 platelet measurements $>50 \times 10^9/L$ between Weeks 6-12. All platelet counts will be reported, and the four measurements closest in time to Weeks 6, 8, 10, and 12 will be selected for the determination of the primary endpoint. Within a sliding one-week window, only one measurement can be selected.

Patients will be classified as non-responders for any of the following reasons:

- 1) Failing to meet the criteria to be a responder (including having an insufficient number of values $>50 \times 10^9/L$ due to missing data); or,
- 2) Requiring rescue medication at any time within the first 12 weeks of therapy; or,
- 3) Withdrawing from protocol therapy prior to week 6.

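### Section 16.b lets an undefined normality test on a binary endpoint choose the primary test, leaving Fisher's exact test as a live fallback to the CMH test named everywhere else

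*Combined protocol and SAP*

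**What the plan says.** Section 5.1 fixes the type of endpoint: "The primary endpoint is binary, with each patient classified as either a platelet responder or a platelet non-responder".

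Section 16.b then makes the choice of test conditional. The analyst is told that "we will first test for normality of the distribution of the proportion of platelet responders". If normality is upheld, a one-sided CMH test at 0.025 is used. "If the normality assumption is violated, then a one-sided" Fisher's exact test replaces it. No normality test, level, criterion or unit (patient, arm, stratum or pooled sample) is given there or elsewhere.

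The same paragraph adds that "The monitoring boundaries and levels of significance for the interim and final analyses of the primary endpoint are detailed in Table 16A", and that in the final analysis "we will reject the null hypothesis if the upper (efficacy) boundary z-value of 1.99302 is crossed".

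Elsewhere only CMH appears. The section 16 Overview names it for the primary objective and refers to 16.b. Section 16.e says "We will conduct two interim analyses using a two-sided Cochran-Mantel-Haenszel test to compare the proportion of platelet responders", and the power statement in 16.f also uses CMH. The Overview stratifies the randomisation by "age at enrollment and up-front treatment status, with block size of 3", but 16.b does not name the CMH strata. Section 16.c repeats the normality check for the secondary endpoints and sends binary ones to Fisher if it fails.

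**The concern.** A confirmatory trial needs one primary test fixed before the data are seen. Here the test depends on a step that has no defined content for a binary outcome, so the analyst's reading of the step decides the test.

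The two tests are not interchangeable. Fisher's test in its standard form ignores the randomisation strata. It yields a p-value, while the final rejection rule is written as a z boundary. The interim analyses use CMH with no fallback, so the Fisher route would also change the test between looks. In a borderline result, two analysts who both follow 16.b could report opposite conclusions. Because the trial is open label, a choice left open until the analysis is harder to defend.

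**Working it through.** **Inputs.** 98 and 49 informative patients (section 4); 108 and 54 randomised, 75% versus 50% response, 9% scored as non-responders (16.f); boundaries 3.7103, 2.51142 and 1.99302 (Table 16A); six strata of at most 27 patients (Table 4A), which is 18:9 at 2:1 allocation.

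**1. The plan's own power figure.** The pooled response rate is (98 × 0.75 + 49 × 0.50)/147 = 2/3. The standard error is √[(2/9)(1/49 + 1/98)] = 0.0825.
- Without continuity correction: drift 0.25/0.0825 = 3.03, three-look power 85.4%.
- With correction ½(1/49 + 1/98) = 0.0153: drift (0.25 − 0.0153)/0.0825 = 2.85, power 80.7%.

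The stated 81.4% corresponds to a drift of 2.872. It lies nearer the corrected version, but the plan does not say whether a correction is used. The boundaries give an overall one-sided level of 0.0250, as intended.

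**2. What the check would select.**
- *On the 0/1 outcomes.* Take Shapiro-Wilk as an example, since the plan names no test. Over every split with at least one responder and one non-responder, the largest p is 2.1e-18 (n = 162), 1.6e-17 (147), 2.6e-10 (54) and 9.2e-10 (49). The check always fails, so Fisher is used.
- *As a pooled large-sample check.* The smallest expected cell is control non-responders: 49 × 1/3 = 16.3, or 54 × 1/3 = 18. CMH is used.
- *As the same check within strata.* A full stratum has 9 controls, so 9 × 1/3 = 3 expected non-responders. With a conventional threshold of 5 (an assumption, since the plan gives none), this could fail and send the analysis to Fisher.

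**3. Borderline tables (108 versus 54, strata ignored).** With m responders in total, d = x − 108m/162 and V = 108 × 54 × m(162 − m)/(162² × 161). Uncorrected z = d/√V; corrected z = (d − 0.5)/√V. For 72 versus 27: m = 99, d = 72 − 66 = 6, V = 8.61.

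| Responders | z uncorrected | z corrected | Fisher one-sided p |
|---|---|---|---|
| 72/108 vs 27/54 | 2.04 (reject) | 1.87 (do not reject) | 0.0305 (do not reject) |
| 71/108 vs 26/54 | 2.15 (reject) | 1.98 (do not reject) | 0.0240 (meets 0.025, fails 0.0231) |

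The limit 0.0231 is the one-sided tail at 1.99302, in line with half the final nominal alpha in Table 16A (0.0463/2).

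**4. Exact power at the final look, strata ignored.** With 9% dilution the rates are 0.91 × 75% = 68.25% and 0.91 × 50% = 45.5%.

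| Setting | CMH uncorrected | CMH corrected | Fisher at 0.0231 | Fisher at 0.025 |
|---|---|---|---|---|
| 147 patients | 85.0% | 79.9% | 79.9% | 81.0% |
| 162 patients | 87.8% | 84.4% | 83.8% | 84.5% |
| 162, 9% dilution | 79.2% | 73.8% | 73.1% | 75.0% |

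At the 0.0231 limit Fisher loses 4.0 to 6.1 points against uncorrected CMH and 0.0 to 0.7 against corrected CMH. Over these settings it disagrees with the uncorrected test in 4.0% to 6.1% of trials and with the corrected test in 0.0% to 0.7%.

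**5. Effect of the strata.** The documents give no stratum-specific rates, so these are assumptions: six strata of 18:9, a 25-point difference in each, 9% dilution, 200,000 simulated trials. Stratified corrected CMH versus pooled Fisher:
- equal control rates: 73.6% vs 73.1% (0.5 points)
- control rates 40% to 60%: 74.3% vs 73.1% (1.1 points before rounding)
- control rates 30% to 70%: 76.8% vs 73.8% (3.0 points)

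**6. Type I error.** Three looks, 162 patients, six equal strata, each route simulated separately. One-sided error is 2.5% for uncorrected CMH, 1.6% for corrected CMH, and 1.5% to 1.9% for CMH interims with Fisher at the final look. With strata ignored, every table that Fisher rejects is also rejected by uncorrected CMH.

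**The case against.** The best defence is that CMH is plainly intended. It is the only test named in the Overview, the interim plan and the power statement, and the final rule is a z boundary. Section 16.b also speaks of the distribution of a proportion, which suggests a check on the normal approximation rather than a test on patient-level 0/1 values. This stands as a reading of intent. But the Overview refers to 16.b for the detail, and 16.b keeps Fisher as an operative branch with an undefined trigger.

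Three stronger readings are tempting and go too far.
- *That the large-sample reading always gives CMH.* This is so only for a pooled check at about the planned rates; a stratum-level check could fail.
- *That the Fisher branch has no significance level.* Section 16.b points to Table 16A, from which 0.0231 follows. An overall level of 0.025 with a smaller final nominal level is normal in a group-sequential design. The limit is implicit, not absent.
- *That Fisher always costs 4 to 6 points.* That loss is against uncorrected CMH, whose 85.4% does not match the stated 81.4%. Against corrected CMH with equal strata it is under 1 point. The continuity correction is a separate unstated choice that matters about as much.

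**Conclusion.** The concern holds as a fault in a stated rule: the step that selects the primary test is undefined for this endpoint, and its plausible readings lead to different tests. The conclusion changes only in borderline results. The power loss is 4 to 6 points or under 1 point, depending on whether the CMH test being replaced is uncorrected or corrected. It is about 1 to 3 points against corrected CMH if control rates vary across strata as assumed above; the true variation is not in the documents.

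A reader might infer that a data-driven choice of test inflates the false-positive rate. The calculations do not support that: no route exceeded the nominal 2.5%, and the Fisher route is conservative. The harm is a primary test that is not fixed in an open-label trial, with possible loss of power. It should be fixed, but it does not invalidate the design.

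**What to change.** In section 16.b, delete the normality pre-test for the primary endpoint. Name CMH stratified by age group and up-front treatment status as the single primary test at all three looks. State whether a continuity correction is used, and compare the signed z with the Table 16A boundaries. Keep any exact test, preferably a stratified one, as a sensitivity analysis that does not affect the primary conclusion.

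For the binary secondary endpoints in 16.c (objectives 3.2.1, 3.2.4 and 3.2.5), do not simply remove the fallback, because some events may be sparse, such as poor bleeding scores at 1 year. Replace the normality test with a pre-stated expected-count trigger for an exact test, giving the threshold and whether it applies to the pooled table or within strata.

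The cost is wording only, with no change to sample size, data collection or boundaries. The change should be made before any comparative analysis of the primary endpoint.
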